7.3 Pregnancy.....	17
8.0 ADVERSE EVENT REPORTING.....	18
8.1 Definitions.....	18
8.2 Reporting.....	19
9.0 STATISTICAL CONSIDERATIONS.....	19
9.1 General Design Issues.....	19
9.2 Endpoints.....	20
9.3 Sample Size and Accrual.....	21
9.4 Monitoring.....	21
9.5 Analyses.....	22
10.0 STUDY MANAGEMENT.....	22
10.1 Institutional Review Board (IRB) Review and Informed Consent.....	22
10.2 Registration Procedures.....	23
10.3 Criteria for Discontinuation.....	23
10.4 Deviations from the Protocol.....	24
10.5 Clinical Site Monitoring and Record Availability.....	24
10.6 Required Documentation.....	24
10.7 Adherence to the Protocol.....	24

10.8	Amendments to the Protocol.....	24
10.9	Data Management.....	24
10.10	Record Retention.....	25
10.11	Obligations of Investigators.....	25
10.12	Participant Confidentiality.....	25
10.13	Study Discontinuation.....	26
11.0	BIOHAZARD CONTAINMENT.....	26
12.0	REFERENCES.....	26

LIST OF ABBREVIATIONS

Abbreviation	Definition
4CMenB	4 component Neisseria meningitidis serogroup B vaccine (trade name Bexsero™)
AE	Adverse Event
CI	Confidence Interval
CTRC	Clinical and Translational Research Center
ID	Identification
Ig	Immunoglobulin
IL	Interleukin
IRB	Institutional Review Board
ISM	Independent Safety Monitor
LOS	Lipo-oligosaccharide
MAb	Monoclonal Antibody
MBRB	Medical Biomolecular Research Building
mL	Milliliter
Ng	Neisseria gonorrhoeae
Nm	Neisseria meningitidis
OMV	Outer Membrane Vesicles
PBMC	Peripheral Blood Mononuclear Cells
TGF	Transforming growth factor
Th	T helper cell
Treg	Regulatory T cell
UNC	University of North Carolina at Chapel Hill
UNCH	UNC Hospitals

PROTOCOL SUMMARY

Protocol Title	Cross-reactive N. gonorrhoeae Immune Responses Induced by a N. meningitidis Vaccine
Study Design	Single arm, prospective clinical trial to assess immunologic responses induced by immunization with 4CMenB vaccine that cross react with N. gonorrhoeae . Participants will receive two-doses of an FDA-approved vaccine that provides protection from N. meningitidis infection according to the recommended dosing schedule. The participants will provide samples of blood as well as mucosal surface derived samples (urine and/or swabs) at four separate visits.
Study Population	Individuals 18-25 years of age that are not pregnant, HIV negative, have no history of congenital immunologic disorder, and are not taking immune suppressive medications
Number of subjects	15
Number of sites	1
Clinical Samples	Blood, pharyngeal swab, urine (male subjects), vaginal swab (female subjects)
Estimated Start of Enrollment	07/31/2019
Estimated Time to Completion	12/31/2020
Protocol Duration	Each individual will participate in the study for between 6 and 8 weeks.
Regimen or Intervention	Each participant will receive two doses of 4CMenB vaccine 5 weeks between doses.

1.0 HYPOTHESIS AND STUDY OBJECTIVES

1.1 Hypothesis

Immunization with 4CMenB induces cross reactive immune responses against *N. gonorrhoeae*

1.2 Primary Objectives

1. Determine whether immunization with 4CMenB induces serum antibodies against *N. gonorrhoeae* surface antigens
2. Determine whether polyfunctional CD4+ lymphocytes directed against *N. gonorrhoeae* surface antigens are induced by immunization with 4CMenB

1.3 Exploratory Objectives

1. Determine whether immunization with 4CMenB induces mucosal surface antibodies against *N. gonorrhoeae* surface antigens
2. Determine whether immunization with 4CMenB induces serum and/or mucosal surface antibodies against *N. gonorrhoeae* porB or mtrE
3. Determine whether immunization with 4CMenB induces serum and/or mucosal surface antibodies against *N. gonorrhoeae* antigens other than porB and mtrE
4. Determine whether polyfunctional CD8+ lymphocytes directed against *N. gonorrhoeae* surface antigens are induced by immunization with 4CMenB
5. Determine quantity and phenotype of CD4+ Tfh cells lymphocytes induced by immunization with 4CMenB
6. Determine inflammatory cytokine production by *N. gonorrhoeae* surface antigen-stimulated PBMC from 4CMenB-immunized humans.
7. Identify and clone B-cell receptors that recognize *N. gonorrhoeae* antigens after immunization with 4CMenB

2.0 INTRODUCTION

2.1 Background

***N. gonorrhoeae* poses global public health threats because of emerging antibiotic resistance.** The WHO estimates over 60 million new cases of *N. gonorrhoeae* (Ng) infection occur each year worldwide, making it one of the most common bacterial sexually transmitted infections¹. Most cases of Ng infection are limited to the lower genital tract, causing urethritis in men and cervicitis in women. Antibiotic resistance in Ng presents a major problem in the control of this pathogen². In 2018, three cases of extensively drug resistant Ng were identified in Australia and the United Kingdom after treatment failure with currently recommended dual antibiotic therapy³. Effective preventative strategies, particularly vaccines, are urgently needed to reduce the public health burden of Ng infections throughout the world.

Ng infection in humans does not lead to protective adaptive immune responses. Uncomplicated Ng infections are associated with increased risk of recurrent infections. Re-infections with the same Ng strain occur at a higher frequency than with other circulating strains in the community, indicating there is little strain-specific immunity to Ng⁴. Moreover, male subjects in experimental human Ng infection studies show no evidence of immunity upon rechallenge⁵.

OMV-based meningococcal vaccines appear to provide cross-species protection against Ng infection. Effective vaccines for the most prevalent serogroups of *N. meningitidis* (Nm) have been in use in humans for decades. Meningococcal vaccines were first generated against polysaccharide capsular antigens of Nm serogroups A,C,Y, and W. Nm serogroup B (NmB) capsule is a poorly immunogenic disaccharide in humans which has made the development of vaccines targeting NmB

challenging and prevented the use of capsular polysaccharide antigen for this purpose⁶. Recently, vaccines containing several proteins and lipoproteins have been generated from NmB OMV^{7,8}. These vaccines are safe and have been used in mass vaccination campaigns in the setting of NmB epidemics in several countries⁹⁻¹¹. STI surveillance in the setting of vaccine campaigns in Cuba and Norway showed reduced rates of Ng infections, which suggested Nm-OMV-based vaccines may offer cross-species protection against Ng^{12,13}. STI education campaigns could have contributed to decreased Ng rates in these settings. However, a recent OMV-based vaccine campaign in New Zealand demonstrated decreased gonococcal infection rates, and surveillance data showed that infection rates for *Chlamydia trachomatis* (another sexually transmitted bacterial pathogen that causes urethritis and cervicitis) did not mirror the decrease in gonorrhea rates. This, and the fact that the effect was greater in vaccinated than unvaccinated persons, strongly supports the hypothesis that the Nm vaccine provided specific protection from Ng infection¹⁴. Data from New Zealand suggest that the Nm-OMV-based vaccine offered ~30% protection against Ng infection. Researchers at the Uniformed Services University of Health Sciences have demonstrated that mice vaccinated with the FDA-approved four component NmB OMV vaccine (4CMenB), delivered subcutaneously (SC) or intraperitoneally (IP), substantially accelerated Ng clearance and reduced vaginal Ng burdens vs. unvaccinated or adjuvant only-treated animals, supporting the ecologic data in humans that suggests Nm-OMV can induce immune responses that protect from Ng. Serum pooled from 10 individual humans that were immunized with 3 doses of 4CMenB and one individual who received the currently US FDA-approved 2 dose schedule of 4CMenB was recently shown to have increased antibody titers against whole Ng bacteria, demonstrating 4CMenB does indeed induce immunologic responses that cross react with Ng¹⁵.

2.2

Rationale

Immunologic responses associated with protection from Nm disease are well-characterized. During a Nm outbreak at a US military base, a lack of detectable bactericidal antibodies against the outbreak strain of Nm was associated with high-rates of invasive infection in exposed individuals¹⁶. Bactericidal antibodies to Nm develop naturally during invasive infection and during nasopharyngeal carriage. Vaccination with capsular polysaccharide, which induced bactericidal antibodies, was shown to protect against invasive Nm disease¹⁶⁻¹⁸. In contrast to Nm, infection with non-encapsulated Ng weakly induces antibodies; anti-Ng antibody concentrations in vaginal secretions and sera are not different in individuals with current or past Ng infection vs. those with no history of infection¹⁹. There are few published studies of Ng-directed T cell responses in patients with Ng, but one small study showed that T cells from 30 Ng-infected patients exhibited weak proliferative responses to gonococcal PorB not significantly greater than proliferation without antigen²⁰. Interleukin 17 (IL-17), the main cytokine from Th17 lymphocytes that stimulates neutrophil (PMN) recruitment and causes local inflammation, increases during Ng infections in humans and mice²¹⁻²³. However, Ng is resistant to PMN killing, leading Russell et al. to suggest that stimulation of adaptive Th17 responses to Ng may partially explain the lack of protective immunity to Ng in humans²².

Identification of the immunologic correlates of protection against *N. gonorrhoeae* would provide critical information that would allow for development and testing of vaccines for the prevention of *N. gonorrhoeae* infection. Characterization of the anti-gonococcal immune responses that develop in response to 4CMenB immunization will provide preliminary data that defines the immunologic parameters that can be assessed in the setting of a clinical trial designed to test the efficacy of 4CMenB or other vaccines for protection against *N. gonorrhoeae* infection. There is currently no data regarding the identity of gonococcal outermembrane antigens recognized by human antibodies after 4CMenB immunization as well as no documented reports of the cellular

immune response evoked by this vaccine. Consequently, this proposed pilot study will provide a crucial first step to defining the immunologic correlates of immunity to *N. gonorrhoeae* infection. Although the 4CMenB vaccine has been FDA approved, it is not currently required for enrollment as a student at the University of North Carolina at Chapel Hill. 4CMenB vaccine uptake has been estimated at 14% based on teen National Immunization Survey data; however, uptake rates between 14% and 98% have been found at Universities that have implemented vaccination campaigns in the setting of NmB disease outbreaks^{24,25}. Thus, it is timely to conduct this study while prior MenB immunization rates in the target population are relatively low.

3.0 STUDY DESIGN

This study is a single center, single arm, interventional pilot study in which participants will receive two-doses of the 4CMenB vaccine according to the recommended administration schedule and will provide blood, pharyngeal swabs, and urine or self-collected vaginal swabs at each of four study visits.

The study population will **include 15 individuals** aged 18-25 years with no contraindication to vaccination and no known immune compromising medical condition or medication.

Participants will be seen for informed consent and eligibility screening. Enrolled participants will be given 1 dose of 4CMenB at enrollment and a second dose at week 5. Participants will be seen at entry, weeks 5, 6, and 7 for blood collection, pharyngeal swabs, and provide urine (male participants) or self-collected vaginal swabs collected for secondary screening and baseline immunologic testing.

4.0 SELECTION AND ENROLLMENT OF PARTICIPANTS

4.1 Inclusion Criteria

1. Able to understand and give informed consent
2. Willingness to undergo all study procedures.
3. Males or females between the ages of 18 to 25 at screening (inclusive).
4. Good health, as determined by medical history and targeted physical exam.
5. Participants agree to abstain from vaccines from study entry to 30 days after receipt of the second 4CMenB vaccine.
6. Female participants of child bearing potential must have a negative urine pregnancy test at the screening visit, and prior to receipt of vaccines at study entry and week 5 visits. Self-reported history is acceptable documentation of hysterectomy, bilateral oophorectomy, tubal ligation, or tubal micro-inserts which eliminate child bearing potential of participant. If participating in sexual activity that could lead to pregnancy, women must agree to use a form of contraceptive until 28 days after completion of the vaccine series. At least one of the following methods must be used appropriately: Condoms (male) with or without spermicidal agent, Diaphragm or cervical cap with spermicide, Intrauterine device (IUD), or Hormone-based contraceptive. Self-report of a monogamous male partner who has a vasectomy is also acceptable.

4.2 Exclusion Criteria

1. Known allergy/sensitivity or any hypersensitivity to latex or any of the components of the study product or its formulation (see section 5.2 for a list of components).
2. Participants who have received any vaccine directed against *N. meningitidis* serogroup B
3. Serious illness or injury requiring hospitalization within 21 days prior to study entry.

4. Current or prior history of a medical condition resulting in impaired immunity (such as HIV infection, inborn or acquired immunodeficiency syndromes, all cancers including leukemia or lymphoma, or the use of antineoplastic drugs or radiation treatment).
5. Known active infection with HIV, HCV, or HBV. This information will be obtained verbally from the participant.
6. History of excessive alcohol consumption, drug abuse, psychiatric conditions, social conditions or occupational conditions that in the opinion of the investigator would preclude compliance with the study.
7. Hemophilia or other bleeding diatheses.
8. Receipt of anticoagulants (aspirin or nonsteroidal anti-inflammatory drugs (NSAIDS) are acceptable) within 14 days prior to study entry.
9. Autoimmune disorders; mild autoimmune disorders, such as eczema, are not exclusionary and will be determined by the investigator.
10. Use of any systemic immunomodulatory treatment, systemic corticosteroids, (inhaled and topical corticosteroids acceptable), investigational products, interleukins, interferons, growth factors, or intravenous immunoglobulin (IVIG) within 45 days prior to study entry.
11. Pregnant women and nursing mothers or women who are planning to become pregnant or breastfeed within 28 days after receipt of their second 4CMenB vaccine.
12. Have received any licensed vaccine within 30 days prior to study vaccination.
13. Have donated blood or blood products within 30 days before study vaccination, plan to donate blood at any time during the study and up to 30 days after the last blood draw.
14. Any condition in the opinion of the investigator that would interfere with the proper conduct of the trial.

4.3 Study Recruitment and Enrollment Procedures

Potential participants will be recruited from the UNC-Chapel Hill University and surrounding area population. Potential participants will be recruited through flyers posted on the campus and through the UNC email listserv and through Join the Conquest at UNC. Potential participants will contact the study team via telephone or email and a study team member will provide information about the study and review eligibility criteria. Participants will receive a total of \$130 over the course of the study to compensate for time and providing samples related to the study in addition to receiving the benefit of protection from invasive *N. meningitidis* infection as a result of receiving the FDA-approved 4CMenB vaccine over the course of the study. The payments for participation are \$20 provided at screening visit, \$20 at entry visit, and \$30 each at week 5 visit, week 6 visit, and week 7 study completion visit. Participants will be paid at the end of each study visit.

To promote a roughly even balance in the sex at birth of participants, enrollment of additional participants of one sex at birth will be discontinued when enrollment of participants of that sex at birth reaches 8 participants.

Once a candidate has been identified, study details will be carefully discussed with the participant by the study coordinator or study investigator. The participant will be asked to read and sign the IRB approved informed consent form. For participants from whom a signed informed consent form has been obtained, a screening visit will be performed that will include obtaining information related to eligibility, completion of a targeted physical examination, and a point of care urine pregnancy test for female participants of child bearing potential. For participants from

whom informed consent has been obtained, but who are deemed ineligible or who do not enroll into initial immunization step, a Screening Failure Results form must be completed.

5.0 STUDY TREATMENT

Study treatment is defined as 4-component *Neisseria meningitidis* group B vaccine, 4CMenB (trade name: Bexsero™)

5.1 Regimens, Administration, and Duration

All participants will receive the 4CMenB vaccine, 0.5 mL, at entry (Day 0) and at week 5. The study product will be administered as supplied, intramuscularly in the deltoid region of the upper arm or the higher anterolateral area of the thigh in the clinic by a licensed study nurse, nurse practitioner, or study physician with experience administering vaccines using aseptic technique during preparation and administration. All injections should preferably be given in the deltoid region and in the non-dominant arm; however, if this is not feasible, the dominant arm may be used. The vaccine must not be injected intravascularly, subcutaneously, or intradermally.

Vaccination should be deferred at the discretion of the site investigator if the participant is febrile or acutely ill. Following each vaccination, a licensed study nurse, nurse practitioner, or study physician with experience administering vaccines will observe the participant for 15 minutes for any adverse reactions/events.

5.2 Study Product Formulation and Preparation

4-Component Meningococcal Group B Vaccine

Each 0.5 mL dose of 4CMenB contains approximately:

• recombinant Neisserial adhesin A protein	50 mcg
• recombinant factor H binding protein	50 mcg
• recombinant Neisserial Heparin Binding Antigen protein	50 mcg
• Outer Membrane Vesicles	25 mcg
• aluminum hydroxide	1.5 mg
• Sodium chloride	3.13 mg
• L-histidine	0.78 mg
• sucrose	10 mg
• Water	quantity sufficient

5.3 Pharmacy: Study Product Acquisition/Distribution and Accountability

5.3.1 Study Product Acquisition/Distribution

4CMenB Vaccine is an FDA-approved product. Study vaccine will be purchased from the manufacturer through UNC Investigational Drug Service (IDS) Pharmacy.

5.3.2 Study Product Accountability

The site pharmacist is required to maintain complete records of all study product received from the manufacturer and subsequently dispensed. All unused study product will be distributed from the UNC Investigational Drug Service (IDS) Pharmacy to the primary investigator's laboratory for use in in vitro experiments after the study is completed or terminated.

5.4 Concomitant Medications

5.4.1 Required Medications

None

5.4.2 Prohibited Medications

- anticoagulants (aspirin or nonsteroidal anti-inflammatory drugs (NSAIDS) are acceptable)
- systemic corticosteroids (inhaled or topical corticosteroids are acceptable)
- systemic antineoplastic drugs
- systemic immunomodulatory drugs (including but not limited to immune modulating monoclonal antibodies, calcineurin inhibitors, antiproliferative agents, mTOR inhibitors, interleukins, interferons, and growth factors)
- investigational or approved vaccines (other than study product)
- intravenous immunoglobulin (IVIG)
- other investigational products

5.4.3 Precautionary Medications

None

6.0 CLINICAL AND LABORATORY EVALUATIONS**6.1 Schedule of Events**

Evaluation	Screening	Entry	48-72 hr post injection	Post-Entry Evaluations			
				Week 5	48-72 hr post injection	Week 6	Week 7
Medical & medication history	X	X		X		X	X
Acute Illness Assessment		X		X			
Vital signs/targeted physical exam	X	X		X		X	X
Pregnancy test ^{1a}	X	X		X			
Phlebotomy collected blood (up to 60 mL per visit)		X		X		X	X
Stored PBMCs ²		X		X		X	X
Stored serum ²		X		X		X	X
Pharyngeal swab collection ²		X		X		X	X
Self-collected vaginal swab ^{1,2}		X		X		X	X
Urine collection ^{2,3}		X		X		X	X
Vaccine injection		X		X			
Telephone contact			X		X		

¹ female participants only^{1a} female participants of child bearing potential² mucosal surface swabs, urine, serum, and PBMC preparations will be used for immunologic analysis that will be conducted on batched samples.³ male participants only**6.2 Timing of Evaluations****6.2.1 Screening Evaluations**

Screening evaluations include: medical history, medication history within the past 60 days, vital signs, targeted physical exam, and pregnancy test for female participants of child bearing potential). Screening visit must be conducted no greater than 30 days prior to enrollment visit. The screening evaluation and enrollment visit can all occur on the same day. Participants may be re-screened one time.

6.2.2 *Entry Evaluations*

Entry evaluations will be collected PRIOR to phlebotomy, specimen collection, and vaccine administration:

Acute Illness Assessment will be completed before phlebotomy, specimen collection, and vaccine administration. Participants who have an acute illness may be rescheduled for their phlebotomy, specimen collection, and vaccine within their screening visit window.

Update medical history and concomitant medications. Conduct a targeted physical exam and collect vital signs [heart rate (HR), blood pressure (BP), oral temperature (Temp), respiration rate (RR), and weight] prior to phlebotomy to collect up to 60 mL of blood, specimen collection, and vaccine administration.

For females of reproductive potential, negative urine pregnancy testing results must be available before phlebotomy, specimen collection, and vaccine administration.

Samples to be stored for immunologic testing will be batch run at the end of the study: pharyngeal swabs, urine sample (from male participants), self-collected vaginal swabs (from female participants), serum, and PBMC.

6.2.3 *Post-Entry Evaluations*

Week 5 Evaluations:

Acute Illness Assessment will be completed before phlebotomy, specimen collection, and vaccine administration. Participants who have an acute illness or who have taken exclusionary anticoagulant medications may be rescheduled for their vaccine within their screening visit window.

Update medical history and concomitant medications before phlebotomy and vaccine administration. Conduct a targeted physical exam and collect vital signs (HR, BP, Temp, RR) before phlebotomy to collect up to 60 mL of blood, specimen collection, and vaccine administration.

For females of reproductive potential, negative urine pregnancy testing results must be available before phlebotomy, specimen collection, and vaccine administration.

Week 5 laboratory evaluations will be collected PRIOR to vaccine administration:

Samples to be stored for immunologic testing will be batch run at the end of the study: pharyngeal swabs, urine sample (from male participants), self-collected vaginal swabs (from female participants), serum, and PBMC.

Week 6 and Week 7 Evaluations:

Update medical history and concomitant medications prior to phlebotomy to collect up to 60 mL of blood and specimen collection.

Samples to be stored for immunologic testing will be batch run at the end of the study: pharyngeal swabs, urine sample (from male participants), self-collected vaginal swabs (from female participants), serum, and PBMC.

6.2.4 *Discontinuation Evaluations*

Participants who elect not to receive or cannot receive the initial immunization or second immunization within the appropriate study time window are permanently discontinued from the study and will have no further evaluations conducted upon discontinuation. Participants who remain eligible but elect to prematurely discontinue from the study will have no additional evaluations performed from the point at which they discontinue. Participants who experience a grade 3 or 4 Adverse Event related to the vaccine or study procedures prior to the second immunization will be discontinued from the study and will return for evaluation at week 6 and/or 7 to ensure resolution but will not provide specimens for immunologic evaluation.

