Pharyngeal and vaginal swabs, urine, and serum for measures of *N. gonorrhoeae*-directed antibodies will be collected per the SOE. Antibodies eluted from swabs or present in urine and present in serum from samples collected at entry, week 5, week 6, and week 7 will be tested for *N. gonorrhoeae* antigen-specific antibodies using ELISA. Antibody containing samples will be sent to Regional Biocontainment Laboratory (RBL) Immunology Unit at Duke University for ELISA analysis. The shipped samples will have an identifying sample number (code) derived from the participant's assigned PID and the visit number; no identifying information on the participant's samples will be transmitted to the Duke RBL Immunology Unit and leftover samples will be destroyed or returned to UNC for storage if the participant has agreed to storage of their study specimens. The PI at UNC will keep a master log which links the codes on the stored specimens to the participants. Leftover sera from consenting participants may be used for future *N. gonorrhoeae* research.

6.3.5 *Vaccine/ Injection*

Every effort should be made to administer vaccines within the protocol-defined visit window. Participants who do not receive their first vaccine within 30 days of screening or who do not receive the week 5 vaccine will be prematurely discontinued from the study.

The week 5 visit should be conducted 35 days (\pm 7 days) after the first vaccination (enrollment visit). If the week 5 visit is not within the protocol-specified window, then the vaccine can be given as late as 8 weeks post enrollment.

The week 6 visit should occur 5-9 days after the second dose of vaccine; if week 6 visit samples are not collected, the participant may continue in the study and attend the week 7 visit 12-16 days after receiving the second dose of vaccine. If the week 7 visit is not collected between day 12-16 after the second dose of vaccine, participant will be discontinued from the study.

Vaccination should be deferred at the discretion of the site investigator if the participant is febrile with reported or observed temperature greater than or equal to 38 °C or acutely ill with symptoms (ongoing or present within 7 days of planned vaccination) consistent with infection of the respiratory tract, gastrointestinal tract, urinary tract, or skin/soft tissues.

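### Section 6.2.3 ties a deferred week 5 dose to the screening window, which has closed by day 35, and no section requires the pregnancy test on the day a deferred dose 2 is given

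*Combined protocol and SAP*

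**What the plan says.** The week 5 part of 6.2.3 covers participants who are acutely ill or who have taken "exclusionary anticoagulant medications may be rescheduled for their vaccine within their screening visit window". The matching sentence for the entry visit, in 6.2.2, reads: "Participants who have an acute illness may be rescheduled for their phlebotomy, specimen collection, and vaccine within their screening visit window". The two differ in what they move: blood, specimens and vaccine at entry, but only the vaccine at week 5.

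The screening window is set in 6.2.1: "Screening visit must be conducted no greater than 30 days prior to enrollment visit". The same section adds: "The screening evaluation and enrollment visit can all occur on the same day". Section 6.3.5 applies the 30 days to dose 1; it discontinues "Participants who do not receive their first vaccine within 30 days of screening".

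Dose 2 has its own timing. Section 6.3.5 puts the week 5 visit at 35 days ± 7 after the first vaccination and continues: "If the week 5 visit is not within the protocol-specified window, then the vaccine can be given as late as 8 weeks post enrollment". Section 10.3.2 lists failure to have dose 2 by 8 weeks as a reason for leaving the study. Section 7.2.2 sends postponement of dose 2 after a Grade 1 or 2 event to 6.3.5.

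A negative urine pregnancy test before dose 2 appears in four places: 4.1 item 6, the Schedule of Events, 6.2.3 and 6.3.3. All four attach it to the week 5 visit. Section 6.2.3 asks that the negative result be on hand before the vaccine. None limits the age of the result or ties it to the day of injection.

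**The concern.** Staff would turn to the 6.2.3 sentence when someone arrives ill, or on an anticoagulant, at week 5. It gives them a limit that has already passed, and it differs from the limit in 6.3.5 and 10.3.2. The wording looks carried over from the entry paragraph, where it fits.

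The vaccine-only wording has a second consequence. If visit and injection fall on the same day, a test attached to the visit is also a test on the dosing day. Once the injection alone may move, that no longer follows. Pregnancy is exclusionary (4.2 item 11) and leads to discontinuation when found (7.3). The safeguard at stake is that dose 2 is not given on the strength of an old negative test.

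**Working it through.** The check is calendar arithmetic. The plan states no figure of its own to reproduce. Day 0 is entry and dose 1.

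**Inputs**
- Screening takes place s days before entry, with 0 ≤ s ≤ 30 (6.2.1; same-day screening gives s = 0).
- The week 5 visit is on day 35 ± 7, so days 28 to 42 (6.3.5).
- The outer limit for dose 2 is 8 weeks = day 56 (6.3.5 and 10.3.2).

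**When the screening window ends**
- Counted generously as 30 days from screening, it ends on day 30 − s. The range is 30 − 30 = day 0 to 30 − 0 = day 30.
- At nominal day 35 it closed between 35 − 30 = 5 and 35 − 0 = 35 days earlier.
- It reaches the week 5 window only if 30 − s ≥ 28, so s ≤ 2, and then only on days 28 to 30. The longest deferral it could allow is 30 − 28 = 2 days.

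If the window is instead taken to end at enrollment, it is closed from day 0 for everyone.

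**Age of the pregnancy test if only the vaccine moves**

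If the week 5 visit and test are on day v and dose 2 is given on the last permitted day L, the test is L − v days old.

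| Visit and test on day | L = 42 (visit window) | L = 56 (8-week limit) |
|---|---|---|
| 28 | 42 − 28 = 14 | 56 − 28 = 28 |
| 35 | 42 − 35 = 7 | 56 − 35 = 21 |
| 42 | 42 − 42 = 0 | 56 − 42 = 14 |

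Both columns are needed because the text does not say which limit governs a deferral from a visit that was itself on time. Section 6.3.5 offers 8 weeks when the visit falls outside its window, whereas 10.3.2 states 8 weeks without that condition.

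**The case against.** The strongest reply is that the protocol already answers both parts. A usable dose 2 window stands in 6.3.5 and 10.3.2, and 7.2.2 points to it, so a careful coordinator would not be misled. A negative test before dose 2 is required in four places, and the Schedule of Events puts test and injection in the same week 5 column. The illness assessment comes before the blood draw, so a deferral would normally be decided before other procedures. Section 6.3.5 treats a late dose as part of a late week 5 visit, and a site that follows that reading would test again on the later day. Contraception is also required (4.1 item 6).

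Much of this stands. The error is an inconsistency in the text, not a missing window, and the test gap opens only if a site completes the visit and then moves the injection alone. But that is the split the 6.2.3 sentence describes. Contraception lowers the risk without replacing the test.

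A reader might infer three stronger claims that the documents do not support.
- **That 6.2.4 would remove these participants.** It refers to those without a "second immunization within the appropriate study time window are permanently discontinued from the study". For dose 2, the appropriate window is the one in 6.3.5 and 10.3.2, so deferred participants still have valid dosing days.
- **That week 5 specimens must move with the vaccine, as at entry.** The text permits a draw during illness but does not require one. Moving it could take the sample outside the 4–6 weeks after dose 1 that define the week 5 time point in 9.2.2. It would also move draws for anticoagulant deferrals, where there is no illness. This is a trade-off for the investigator.
- **That the symptom rule in 6.3.5, "symptoms (ongoing or present within 7 days of planned vaccination", pushes dose 2 past day 42.** That depends on when symptoms end, deferral is at the investigator's discretion, and with an 8-week limit in the text day 42 is not a firm stop.

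**Conclusion.** The concern holds as a minor inconsistency with a narrow safety gap. The rescheduling limit in 6.2.3 is wrong: it belongs to dose 1 and has expired for every participant by nominal day 35. The missing dosing-day requirement leaves room for a pregnancy test up to 14 days old at dose 2 under a day 42 limit, or up to 28 days old (21 from a nominal visit) under the 8-week limit.

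These figures assume that day 0 is dose 1, that the screening window runs 30 days from screening, and that a site defers the injection alone without retesting. They are upper bounds. The documents give no deferral rate, so the number of women affected cannot be estimated; enrollment is up to 15 in all.

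The primary comparisons use entry and week 7 samples, and the week 7 visit is timed from dose 2 itself (12–16 days after it, 6.3.5), so nothing here disturbs them.

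**What to change.** 1. In 6.2.3, replace the reference to the screening visit window with: *within the dose 2 window in 6.3.5, and no later than 8 weeks after dose 1*.
2. In 6.2.3 and 6.3.3, add: *A negative urine pregnancy test is required on the day dose 2 is actually given.* As now, this applies to women of child-bearing potential.

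The cost is a changed cross-reference and one added sentence in an amendment, plus one repeat point-of-care urine test for each deferred woman of child-bearing potential. Section 4.3 stops enrollment of either sex at 8, so even if every woman were deferred once this would be about 8 tests. No visit, assay or analysis changes.
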